# b. Secondary outcome variables.

Acceptability:

- Percent of participants who would recommend their medication to a family member or friend trying to taper down from opioid medications
- Visual analog ratings of the degree to which the medication suppressed opioid withdrawal symptoms
- Participant rating of medication acceptance on a 5-point acceptance rating scale
- Attentional bias measured by the visual probe task and the cue-concurrent choice task
- c. Statistical plan including sample size justification and interim data analysis.

This is a within-subject pilot study to support an R01 trial. Results will be primarily evaluated descriptively because the study will not be sufficiently powered or designed for formal betweengroup testing. Outcomes described above will be used as preliminary data within an R01 application.

d. Early stopping rules.

Participants will be discharged from the study if they leave the residential unit against medical advice, request to be removed from the study, express suicidal thoughts, are noncompliant with study tasks, or if new information becomes available to suggest this study may cause them more than minor harm.

The study will be stopped if any of the following criteria are met: 1) participant death during participant or 2) five participants have AST/ALT values 3X ULN at the end of the study relative to baseline (collected at screening) levels.

#### 8. Risks

a. Medical risks, listing all procedures, their major and minor risks and expected frequency.

Risks Associated with Cannabidiol: Cannabidiol has few contraindications. It should not be administered to persons with known sensitivity to cannabidiol. Epidiolex is extensively metabolized by the liver, therefore persons with moderate-severe hepatic impairment (defined in the FDA product label as ALT or AST levels >3x ULN and/or Bilirubin levels >2x ULN) who might have different plasma concentrations of Epidiolex as a result of liver impairment will also be excluded. Epidiolex has been reported to produce somnolence or sedation in up to 32% of patients (compared to 11% of patients receiving placebo) and this may be further exacerbated in persons who are taking other CNS depressants. The FDA also recommends that persons receiving any antiepileptic drug, of which Epidiolex is one, be screened for suicidal behaviors prior to beginning drug administration. Additional side effects reported in clinical trial examinations of Epidiolex for seizure indications in adult and child populations include decreased appetite, diarrhea, weight decrease, gastroenteritis, lethargy, fatigue/malaise, insomnia, irritability/agitation, drooling, gait disturbance, rash, hypoxia, and infections. A determination of the safety of CBD during pregnancy has not yet been made.

Risks Associated with Methadone: The risks associated with methadone are well known and it is notable that we will not be administering any dose of methadone that is higher than the dose the participant already receives as part of his or her routine methadone maintenance treatment. The potential acute side effects of methadone relevant to our protocol include constipation, nausea, sleepiness, vomiting, tiredness, headache, dizziness, and abdominal pain. Like other opioids, methadone is contraindicated in patients with respiratory depression or acute bronchial asthma or hypercarbia.

Both methadone and Epidiolex are metabolized by CYP3A4. Although methadone will not be co-administered with Epidiolex, it is possible that methadone may still be undergoing metabolization early in the study because of its long half-life. We will monitor for any adverse events and believe there will be little risk of negative interactions because Epidiolex will be titrating up as methadone plasma levels are decreasing. The most likely effect is that participants will experience a more delayed onset in withdrawal from methadone, which we will be able to visualize as a result of our placebo control condition.

b. Steps taken to minimize the risks.

Protection against Epidiolex risks: We have experience in the administration of study medications in laboratory settings and therefore anticipate few problems. Participants will be informed of the potential side effects and risks associated with the study drug administration. Participants will be free to discontinue study participation at any time without consequence. We will also conduct psychiatric screening during the Screening session to ensure that patients with current or history of psychiatric events, namely history of suicidality, are excluded from study participation. Further, all participants will be informed about the potential side effects of the study medications and will be permitted to end study participation at any time if they experience negative events, with no consequences. Both methadone and Epidiolex are metabolized by CYP3A4. Although methadone will not be co-administered with Epidiolex, it is possible that methadone may still be undergoing metabolization early in the study because of its long half-life. We will monitor for any adverse events and believe there will be little risk of negative interactions because Epidiolex will be titrating up as methadone plasma levels are decreasing. The most likely effect is that participants will experience a more delayed onset in withdrawal from methadone, which we will be able to visualize as a result of our placebo control condition.

Protection Against Methadone Risks: Our group has experience in the administration of methadone and other opioids in laboratory settings and anticipate few problems. Importantly, we will not administer methadone in amounts greater than what is normally prescribed to the participant. All drug administration will take place at the residential research unit under supervision of medical and research staff.

c. Plan for reporting unanticipated problems or study deviations.

All study events will be monitored during weekly meetings between the study investigators and we will follow all IRB guidance and recommendations regarding the reporting of unanticipated problems of study deviations. All such problems and deviations will be documented and if they do not meet the criteria for immediate reporting, they will be submitted to the IRB as part of the continuing review (or when otherwise requested).

d. Legal risks such as the risks that would be associated with breach of confidentiality.

Participants are all receiving methadone for the purpose of OUD outside of the study activities, and we do not believe this study poses any legal risks associated with breach of confidentiality.

e. Financial risks to the participants.

Participants will not incur any cost for study participation. All study medications will be provided to them at no cost.

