that morning. After collecting vitals and testing a urine sample for pregnancy and to confirm abstinence from illicit drugs, participants will receive 50% of their prescribed methadone dose, which will be prepared by the BPRU pharmacy, to consume under staff observation at BPRU. This dose will produce modest suppression of participant opioid withdrawal for an acute period of time, which will provide an opportunity for them to become acquainted with the session procedures while still ensuring they will show prominent signs of withdrawal during the study period. Initial vitals and urine testing will take place at the BPRU. The participant then will be transferred to the CRU where they will remain until the end of the 3rd day. Participants will be assessed for symptoms of opioid withdrawal and complete measures of drug craving and anxiety periodically throughout Day 1. The first dose of study drug (placebo or Epidiolex) will be administered in the afternoon (e.g., 18:00 +/- 1:00 hour) on Day 1 at the CRU.

Participants will complete withdrawal ratings on a regular basis (e.g., every 4 hours) before and after study drug administration, except for when the participant is sleeping. This schedule will be based on the pharmacokinetic profile of CBD (21). Vital signs will also be measured every time withdrawal assessments occur (Figure 1).

[figure not shown]

Figure 1. Timeline of inpatient session with approximate timing for study procedures. Gray circles indicate when measures of opioid withdrawal. craving. and anxietv are assessed.

On Day 3, participants will complete a cue-induced craving task and a Cue-concurrent Choice Task, and a Methadone Valuation Task described below. Withdrawal ratings will continue up to study discharge on Day 3 and acceptability ratings of the study drug will be collected prior to discharge. Participants will be discharged in the afternoon on Day 3, one hour after finishing the Methadone Valuation Task. At any point a participant can elect to resume regular methadone dosing and remain at the unit to complete study participation. However, participants who take their dose before beginning the Methadone Valuation Task he or she will not be able to participate in the Methadone Valuation Task. Finally, before participants leave, medical staff will collect a blood sample to be tested for liver enzyme levels. For an overview of study procedures, please reference Figure 1.

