Cue-concurrent Choice Task: The effects of opioid-related cues on concurrent choice will be evaluated using a cued concurrent choice task. Participants will be instructed that they will be asked to make choices about different amounts of money that they would like to earn. Participants will be instructed that they should consider the choices carefully because they will randomly receive five of the monetary outcomes they chose. This task consists of a series of trials in which concurrent choice is evaluated between two monetary values (e.g., \$0.10 versus \$0.05). Each concurrent choice is immediately preceded by two visual stimuli presented side-by-side. On opioid trials, one image is opioid-related and the other is a paired neutral image. Opioid-related images include depictions of prescription pills or heroin and/or related drug paraphernalia. Paired neutral images are chosen to match the number of objects, color, and size of opioid images. On neutral filler trials, both images are unrelated to opioids or opioid paraphernalia (e.g., furniture pieces). All trials begin with a fixation point presented for 1000 ms in the center of the screen. The two visual stimuli then replaced the fixation point and are displayed for 2000 ms. Finally, a monetary value appears below each image and participants are instructed to select the monetary reinforcer they want to receive. Participants will receive their money choices from 20 random trials which could earn them an additional \$5. Potential earnings will be explained prior to starting the task to increase engagement with the task.

Methadone Reinduction: At the end of the Methadone Valuation Task, all participants who have not yet requested the methadone dose will receive their dose. All Day 3 methadone doses will be 50% of the participant's prescribed dose. Participants will be required to remain on the unit under observation until 17:00 to provide sufficient opportunity for peak effects of methadone to occur. At 17:00, all participants who show no signs of respiratory distress (SP02<96, respiration rate <8 breaths per minute) and feel safe to leave will be discharged. Any participant who is unable to leave will be observed until he/she is safe ot

leave or will be readmitted to the CRU one additional night. Participants will be expected to return to routine care upon methadone reinduction and study discharge.

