Following oral administration, the bioavailability of methadone ranges between 36 to 100% and peak plasma concentrations are achieved between 1 and 7.5 hours. Published reports indicate that after multiple dose administration the apparent plasma clearance of methadone ranged between 1.4 and 126 L/h, and the terminal half-life (T1/2) was highly variable and ranged between 8 and 59 hours in different studies. Methadone undergoes hepatic N-demethylation by cytochrome P450enzymes, principally CYP3A4, CYP2B6, CYP2C19 and to a lesser extent by CYP2C9 and CYP2D6. Since methadone is lipophilic, it has been known to persist in the liver and other tissues. The slow release from the liver and other tissues may prolong the duration of methadone action despite low plasma concentrations.

b. Justification and safety information if FDA approved drugs will be administered for non-FDA approved indications or if doses or routes of administration or participant populations are changed.

*Cannabidiol:* Cannabidiol is a constituent of the cannabis plant that is being actively investigated for efficacy in a wide range of potential indications (including anxiety and alcohol/substance use disorders, as evidenced by clinicaltrials.gov entries) because of its unique pharmacological mechanisms of action. Specifically, it acts as an inverse agonist on the cannabinoid CB1 and CB2, as a 5-HT1a agonist, as a positive modulator of the transient receptor vallinoid-1 (TRPV1) receptor, and as an allosteric modulator of the mu and delta opioid receptors. The only empirical human studies that have examined the effects of cannabidiol in the context of opioid use reported that cannabidiol can reduce opioid craving and associated anxiety in persons with opioid use disorder. There is preclinical support that the endocannabinoid system is influential in the expression of opioid withdrawal. Cannabinoid type 1 (CB1) receptors are co-localized with mu-opioid receptors and cannabinoid agonists and endocannabinoid catabolic enzyme inhibitors have all shown evidence for opioid withdrawal suppression. Furthermore, over the last 40 years, preclinical evidence has accumulated indicating that CBD can mitigate symptoms of opioid withdrawal and decrease opioid seeking behavior in rodent models. Together these data suggest that CBD warrants further examination as a legitimate treatment for opioid withdrawal symptoms. Safety studies have demonstrated

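### The low-interaction rationale in section 8 does not cover methadone re-dosing on Day 3, and no rule says what happens to the remaining study drug when methadone is resumed early

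*Combined protocol and SAP*

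**What the plan says.** **Risk text (sections 8a and 8b, same wording in both).** The two drugs share a CYP3A4 pathway. The text continues: "Although methadone will not be co-administered with Epidiolex, it is possible that methadone may still be undergoing metabolization early in the study". The reason given for low risk is that "there will be little risk of negative interactions because Epidiolex will be titrating up as methadone plasma levels are decreasing". No later overlap is discussed.

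**Study drug (section 4a, Session Procedures).** There are four doses of 800 mg, 12 hours apart. The first "will be administered in the afternoon (e.g., 18:00 +/- 1:00 hour) on Day 1 at the CRU". Four doses are said to bring Epidiolex to steady state.

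**Methadone (section 4a).** Half the prescribed dose is given on the morning of Day 1. On Day 3 methadone is offered from the morning, during the Methadone Valuation Task, and anyone who has not asked for it by the end of the task (14:00) then receives it. "All Day 3 methadone doses will be 50% of the participant's prescribed dose". Section 6a adds that the Day 2 dose is omitted.

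**Early resumption (section 4a, Session Procedures).** "At any point a participant can elect to resume regular methadone dosing and remain at the unit to complete study participation". Anyone who takes methadone before the task starts is barred from it. Neither the removal criteria (section 4f) nor the stopping rules (section 7d) mention early resumption.

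**Observation on Day 3.** The task and Methadone Reinduction paragraphs say: "Participants will be required to remain on the unit under observation until 17:00 to provide sufficient opportunity for peak effects of methadone to occur". Release is conditional on a check of breathing and on how the participant feels: "all participants who show no signs of respiratory distress (SP02<96, respiration rate <8 breaths per minute) and feel safe to leave will be discharged". Anyone not fit to go is observed further or kept another night. Session Procedures instead puts discharge one hour after the task ends.

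**The concern.** The single argument offered for low interaction risk depends on methadone falling. On Day 3 the plan gives methadone again, when Epidiolex is expected to be at steady state, so methadone is rising. This reaches every participant who completes the active session. Section 8a itself reports somnolence or sedation in up to 32% of patients on Epidiolex against 11% on placebo, and notes that other CNS depressants may add to it.

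The early-resumption clause leaves staff to guess. Some may continue study drug after methadone and others may stop it. Adverse-event frequency by condition is a primary safety outcome (section 7a), and early resumers would contribute to it under an undefined mix of the two drugs.

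The same clause affects efficacy. The number of intervals in which money is chosen over methadone is a primary efficacy outcome. Barring those who took methadone first, with no scoring rule, removes the participants who most wanted it.

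**Working it through.** **1. Time of the fourth study dose.** Inputs: first dose 18:00 on Day 1 (an example time, with a one-hour window) and a 12 h interval, both from Session Procedures.
- Dose 4 = 18:00 on Day 1 + 3 × 12 h = 06:00 on Day 3.
- If the one-hour window carries through: 05:00 to 07:00.

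**2. Gap to Day 3 methadone.** Input: latest methadone time 14:00.
- 14:00 − 06:00 = 8 h (7 to 9 h with the window). Anyone who asks earlier has a shorter gap.

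**3. Where each drug is in its course.** Section 6a gives an Epidiolex peak at 5 to 6 h for 750 mg, the nearest dose reported. For methadone, "peak plasma concentrations are achieved between 1 and 7.5 hours".
- Epidiolex: 06:00 + 5 to 6 h = 11:00 to 12:00, which is 2 to 3 h before 14:00 (1 to 4 h with the window).
- Methadone taken at 14:00: 14:00 + 1 to 7.5 h = 15:00 to 21:30.
- Supporting check: a one-compartment model of four doses, with half-life 8 to 9 h (reported at 200 mg and assumed to hold at 800 mg). For the 18:00 start, Epidiolex at 14:00 is about 83 to 88% of its session maximum with a single-dose time to peak of 5 to 6 h. It is about 65 to 68% with 2.5 h, the middle of the range reported at 200 mg.

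On either set of values Epidiolex is still substantial when methadone starts to rise. This is the reverse of the pattern that section 8 relies on.

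**4. Length of observation after a 14:00 dose.**
- To 17:00: 3 h, which is 21:30 − 17:00 = 4.5 h before the latest stated peak.
- Under the one-hour rule: 14:00 + 1 h = 15:00, which is 6.5 h before the latest stated peak and level with the earliest.

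**5. Early resumption.** If study drug continued, the amount still to come would be:
- after dose 1: 3 × 800 = 2,400 mg
- after dose 2: 2 × 800 = 1,600 mg
- after dose 3: 800 mg

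On Day 1, 50% of the methadone dose has already been taken. A full regular dose would bring the day to 50% + 100% = 150%, against the section 8b commitment not to exceed what is prescribed. The consistent ceiling is 100% − 50% = 50%.

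**6. Valuation task.** Let f be the fraction of sessions barred in a condition and m the mean count among those who do the task. Counting barred sessions as zero, the mean over all sessions is (1 − f) × m. If m is the same in both conditions, the task-takers alone show m − m = 0. Over all sessions the difference is (1 − f for CBD) × m − (1 − f for placebo) × m = (f for placebo − f for CBD) × m. Any difference in barring between conditions is therefore invisible among task-takers. The documents give no value of f, so the size is unknown.

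**The case against.** **A reader might infer that the statement about co-administration is false for the planned schedule.** The documents do not support that. Methadone is scheduled for the morning of Day 1 and the Day 3 task window, study drug from about 18:00 every 12 h, and no scheduled methadone dose coincides with a study dose. On a narrow reading of the term, the schedule complies. What fails is the reason given for low risk, and the limit of overlap to the early part of the study. The exposure is not hidden: section 4a sets out the Day 3 dose, and section 9a describes the study as informing on the combination.

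**A reader might infer an uncontrolled hazard on Day 3.** That is also too strong. Scheduled methadone over the three days is 50% + 0% + 50%, one daily dose in place of three. The Day 3 dose is half of one held unchanged for at least 2 weeks (section 5). Discharge depends on saturation and breathing rate, with an extra night available. Section 6b cites tolerability of CBD with fentanyl. The 4.5 h shortfall uses the far end of a wide range. All of this stands, and none of it repairs the rationale. The observation safeguard is itself weakened by the one-hour discharge sentence.

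**A reader might infer that early resumption necessarily leads to concurrent dosing.** It does not: completing participation need not mean taking more study drug, and section 8 could be read as forbidding it. The text is silent, so it permits either course. The milligram figures in step 5 apply only if dosing continues.

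**On scoring.** Barred participants were never offered money in the task, so zero is a convention. The analysis is mainly descriptive (section 7c), and the first feasibility outcome counts those who complete as intended. These points are fair, and they are why the count per condition should accompany the score.

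**Conclusion.** The concern holds in limited form. The low-interaction reasoning in section 8 does not cover Day 3, when every completer of the active session receives half a methadone dose about 8 h or less after the fourth study dose. The plan also permits, without requiring, concurrent dosing after early resumption, because no rule addresses the remaining study drug.

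The gap in the text is certain. The clock times are derived from an example start, and the session timeline figure is not available here. The Epidiolex timing borrows from 750 mg and 200 mg data. The hazard is partly managed, and the documents allow no estimate of the size of any interaction. The valuation-task exclusion is related to the outcome, but its effect cannot be sized.

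Section 6a names only the Day 1 dose as reduced, although Day 3 is also 50%. A reader might take this as a second contradiction, but the same paragraph allows the prescribed dose or less, so it is an editorial clean-up only.

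**What to change.** 1. **Study drug on early resumption.** State that remaining study-drug doses stop once methadone is resumed early, and cap a Day 1 resumption at the other 50% of the prescribed dose. The cost is the lost study-drug exposure in those participants. The clinical choice is the sponsor's; if dosing is to continue, the risk text and monitoring must cover concurrent use.
2. **Risk text and discharge.** Revise the statements in 8a and 8b to cover Day 3 re-dosing. Remove the one-hour discharge sentence in favour of 17:00 or later, considering whether 17:00 is late enough after a 14:00 dose. A later time would cost staff hours.
3. **Task scoring.** Score participants barred from the Methadone Valuation Task for taking methadone first as zero money-over-methadone intervals, and report their number per condition. Zero is the same whether intervals are 30 minutes (section 7a) or 60 minutes (section 4a).
4. **Clean-up.** Align the section 6a dose description with the 50% Day 3 dose.

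This is a wording amendment with one dosing rule, one dose cap and one scoring rule. It adds no visits.
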